APPENDIX C. PHARMACOKINETIC ANALYTICAL PARAMETERS

C_{ave}	Average steady-state plasma concentration ($AUC_{0-12h}/12h$ or $AUC_{0-24h}/24h$)
C_{max}	Maximum observed plasma concentration
C_{min}	Minimum observed plasma concentration during the dosing interval
T_{max}	Time to maximum plasma concentration
AUC_{0-t}	Area under the single-dose plasma concentration-time curve from Hour 0 to the last quantifiable measurable plasma concentration, calculated by the linear trapezoidal rule for increasing concentrations and the log trapezoidal rule for decreasing concentrations
$AUC_{0-\tau}$ (ie, AUC_{0-12h} or AUC_{0-24h})	Area under the steady-state plasma concentration-time curve over 1 dosing interval (ie, from Hour 0 to 12 for BID administration or from Hour 0 to 24 for QD administration), calculated by the linear trapezoidal rule for increasing concentrations and the log trapezoidal rule for decreasing concentrations
λ_z	Apparent terminal phase disposition rate constant, where λ_z is the magnitude of the slope of the linear regression of the log concentration versus time profile during the terminal phase
$t_{1/2}$	Apparent plasma terminal phase disposition half-life (whenever possible), where $t_{1/2} = (\ln 2) / \lambda_z$
Cl/F	Oral dose clearance
V_z/F	Apparent oral dose volume of distribution
Fluctuation	Steady-state fluctuation ($(C_{max} - C_{min})/C_{ave}$)

In addition, the following PK parameters may be calculated, whenever possible, for each subject:

A_e	Amount of drug excreted in the urine over sampling interval
Cl_r	Renal clearance, where $Cl_r = A_e/AUC$
% Excreted or f_e	percent excreted in the urine, where % Excreted = $100 (A_e/\text{dose})$

Pharmacokinetic calculations will be performed, if appropriate, using commercial software such as WinNonlin[®] (Pharsight Corporation, Cary, NC). Additional details of analyses will be described in the statistical analysis plan.

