5.2. Study Drug

5.2.1. Description and Administration

The study drug (INCAGN01876) is in liquid form in the formulation buffer of 10 mM histidine, 7% sucrose, pH 6.0 at a strength of 10 mg/mL to be used for IV infusion. The infusion site should not be used for blood sampling.

Study drug will be diluted in 0.9 % normal saline and administered by qualified personnel as an IV infusion over a 30-minute period on Day 1 of each cycle. In Part 1, subjects will be administered study drug, according to cohort enrollment ([Table 2](#)). In Part 2, subjects will be administered study drug at the RP2D and schedule. Subjects will continue to receive INCAGN01876, up to the defined maximum number of cycles, as long as the subject is deriving benefit and has not met any of the Protocol-defined conditions for treatment withdrawal (see [Section 5.5](#)).

Duration of treatment (maximum number of cycles) will be determined based on safety during Part 1 and may be fewer than the absolute maximum number of cycles as outlined below:

- For a 14-day cycle: maximum of 26 cycles
- For a 21-day cycle: maximum of 17 cycles
- For a 28-day cycle: maximum of 13 cycles

The Pharmacy Manual contains additional information and instructions for study drug preparation and infusion.

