9.4.3. Pharmacokinetic Analysis

The PK parameters of C_{max} , t_{max} , C_{min} , and AUC_{0-t} (INCAGN01876) will be summarized by part, dose, and study cycle. The log-transformed PK parameters will be compared among dose levels by using a 1-factor analysis of variance. Dose-dependent parameters (C_{max} and AUC) will be normalized to the lowest common dose before statistical comparisons. Additionally, if sufficient data are available, then the dose proportionality of INCAGN01876 C_{max} and AUC will be evaluated statistically by using a power model (eg, $AUC = \alpha \cdot (\text{dose})^\beta$) or equivalently $\log(AUC) = \log(\alpha) + \beta \cdot \log(\text{dose})$, where linear dose proportionality is accepted if β is not significantly different from 1). Refer to Appendix C for a detailed list and description of the PK parameters.

If there is a sufficient amount of plasma concentration data from this study, then the data will be analyzed by standard population PK methods using appropriate software (eg, NONMEM).

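### Protocol Appendix C defines Cave, AUC0-tau and fluctuation over 12 or 24 h for an oral BID or QD drug, so these three parameters come out wrong for an IV antibody given every 14 to 28 days; the four named PK endpoints do not use that window

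*Protocol*

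**What the plan says.** Protocol Section 9.4.3 names Cmax, tmax, Cmin and AUC0-t for summary by part, dose and cycle. It plans an ANOVA on dose-normalized values and a power model, both using an AUC without a subscript. It then says: "Refer to Appendix C for a detailed list and description of the PK parameters".

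Appendix C contains the following:

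- AUC0-tau is the "Area under the steady-state plasma concentration-time curve over 1 dosing interval", but a bracket beginning with 'ie' fixes that interval as "from Hour 0 to 12 for BID administration or from Hour 0 to 24 for QD administration".
- Cave, the "Average steady-state plasma concentration", is AUC0-12h/12h or AUC0-24h/24h, with no other option.
- "Steady-state fluctuation" is (Cmax − Cmin)/Cave, so it inherits the Cave window.
- Cl/F is "Oral dose clearance" and Vz/F is "Apparent oral dose volume of distribution".
- Urinary excretion and renal clearance are listed separately, as optional.

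The drug is given as an "IV infusion over a 30-minute period on Day 1 of each cycle" (Protocol Section 5.2.1), with cycles of 14, 21 or 28 days. Section 1.2.2 describes it as a human IgG1 antibody.

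Appendix C leaves further analysis detail to the SAP. SAP Section 7.6 repeats the four parameters and the models of Section 9.4.3. It defines neither tau, AUC0-tau, Cave nor fluctuation.

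**The concern.** The appendix appears to have been carried over from an oral drug taken once or twice a day. The route, the interval and the clearance terms all fail to fit this product. Only the urine items are marked as optional, so an analyst who follows the appendix literally would compute Cave, AUC0-tau and fluctuation from the first 12 or 24 h of an interval lasting 336 to 672 h.

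The 24 h version can be run on the planned Cycle 6 samples (preinfusion, postinfusion, 4 h, 24 h), so it would yield plausible numbers and nothing would flag the error. A value labelled as average steady-state concentration would really be the average over the first day, close to the peak. The error also grows with cycle length. It would therefore distort any comparison of Cave between schedules, and Part 1 is meant to choose a schedule partly on PK.

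**Working it through.** **1. Reproduce the protocol's own Cave.** The Table 1 footnote gives AUC = 3790 μg·h/mL at 1 mg/kg in monkeys dosed weekly.

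- Cave = 3790/(7 × 24) = 22.56 μg/mL (stated 22.6).
- Mean EC50 = (3.0 + 1.9 + 3.3 + 3.5 + 2.0)/5 = 2.74 μg/mL (stated 2.7).
- Dose equivalent = 2.7/22.6 = 0.119 mg/kg (stated 0.12).

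The divisor is the full 168 h dosing interval. Section 1.3.1 therefore uses the usual definition and Appendix C does not.

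**2. Effect of the 24 h window in this trial.** The documents give no human half-life. I assume mono-exponential decline with a half-life of 7 to 20 days, k = ln 2/half-life per day, and neglect the 30-minute infusion. With tau in days:

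- Fraction captured = AUC0-24h/AUC0-tau = (1 − e^(−k))/(1 − e^(−k·tau)).
- Cave inflation = (AUC0-24h/1 day)/(AUC0-tau/tau) = tau × that fraction.

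For half-life 7 d and tau = 14 d: 0.09428/0.75 = 0.1257, and 14 × 0.1257 = 1.76. For half-life 20 d: 0.03406/0.38443 = 0.0886, and 14 × 0.0886 = 1.24.

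| Half-life | AUC0-24h as share of AUC0-tau, 14 d | Cave inflation, 14 d | 21 d | 28 d |
|---|---|---|---|---|
| 7 d | 12.6% | 1.76 | 2.26 | 2.82 |
| 10 d | 10.8% | 1.51 | 1.83 | 2.19 |
| 14 d | 9.7% | 1.35 | 1.57 | 1.80 |
| 20 d | 8.9% | 1.24 | 1.38 | 1.54 |

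The 12 h window, (1 − e^(−k/2))/(1 − e^(−14k)), captures 6.4% to 4.5% of the 14-day AUC0-tau. Protocol Table 13 has no 12 h sample, so that figure has no direct measurement behind it.

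**3. Fluctuation.** Cmax and Cmin over the real interval are unchanged, so (Cmax − Cmin)/Cave falls by the same factor. In this model the correct value is k·tau. At half-life 14 d and tau = 14 d that is 0.69, and with the 24 h Cave it is 0.69/1.35 = 0.51.

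**4. Sensitivity.** A one-compartment model at steady state with the 30-minute infusion included gives nearly the same results (1.75 at half-life 7 d, tau 14 d). Over half-lives of 3 to 21 days and cycles of 14 to 28 days, the 24 h Cave inflation runs from 1.22 to 5.73. The direction holds for any half-life, because concentrations fall after the infusion.

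**The case against.** The strongest reply is that no planned output is shown to use the faulty definitions. The PK endpoints are Cmax, tmax, Cmin and AUC0-t. AUC0-t runs to the last quantifiable concentration, and Cmin refers to the dosing interval without giving hours. In the unredacted text, Cave, AUC0-tau and fluctuation have no planned summary, test or decision rule. This stands, and it limits the reach of the point.

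The second reply is that the AUC0-tau entry also says one dosing interval, which is right here, and that its hours apply only to BID or QD dosing, which this trial does not use. That has some force for AUC0-tau. It does not help Cave, whose formula offers only 12 or 24 h, or fluctuation, which depends on Cave.

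A reader might infer more than the documents support:

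- **That dose proportionality is corrupted.** The AUC without a subscript follows a list in which AUC0-t is the only AUC. Under the linear model above, a 24 h AUC would be a constant fraction across doses for a given half-life and schedule, leaving the power-model slope unchanged. What remains is an ambiguity. Appendix C calls AUC0-t a single-dose quantity, yet the summaries are by cycle.
- **That human Cave will be set against the 2.7 μg/mL EC50 to judge a pharmacologically active dose.** No section plans this. Table 1 supports the starting dose using monkey exposure, and the definition of the pharmacologically active dose is partly redacted.
- **That a 24 h Cave barely responds to the schedule.** At steady state its 14-day to 28-day ratio is 1 + e^(−14k), which is 1.25 at half-life 7 d and 1.62 at 20 d. The true ratio is 2.0, so the contrast is blunted but still present.
- **That there is no urine PK sampling.** None is visible, but Tables 9 and 13 are partly redacted.

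**Conclusion.** The point holds for Cave, AUC0-tau and fluctuation. Appendix C states a rule that does not fit this drug, Section 9.4.3 refers to it, the SAP does not repair it, and Table 1 contradicts it. Calculated as written on a 14-day cycle, AUC0-24h would be about 13% to 9% of AUC0-tau, Cave would be 1.76 to 1.24 times too high, and fluctuation would be too low by the same factor. On a 28-day cycle the Cave inflation is 2.82 to 1.54. These sizes rest on an assumed half-life of 7 to 20 days and mono-exponential decline, and a distribution phase would make them larger.

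It does not follow that the secondary PK endpoints are wrong, or that a dose, stopping or safety decision depends on these values. This is a definition error worth correcting before any of the three parameters is reported.

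**What to change.** Rewrite Appendix C for cyclic IV dosing:

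- Define tau as the assigned cycle length: 336, 504 or 672 h.
- Define AUC0-tau in Cycle 6 from Hour 0, the start of infusion, using the preinfusion sample, then the postinfusion, 4 h, 24 h and Day 7 samples, up to tau.
- Use actual sample times, and interpolate or extrapolate to tau when the Cycle 7 Day 1 preinfusion sample is off its nominal day. That visit has a ±3-day window, so on a 14-day cycle the sample may fall about 11 to 17 days after the Cycle 6 dose. Protocol Section 7.8.2 and SAP Section 7.6 keep nominal times for samples beyond 4 h, so this needs an explicit exception there.
- Set Cave = AUC0-tau/tau, with fluctuation based on that Cave.
- Rename Cl/F and Vz/F as CL and Vz. Delete the BID/QD and oral wording, and delete the urine items unless urine PK sampling exists in the redacted text.
- State in Section 9.4.3 and SAP Section 7.6 which AUC enters the ANOVA and the power model.

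The cost is appendix wording at the next amendment and matching lines in the SAP. No new visits or samples are needed. The Cycle 6 Day 1, Day 2 and Day 7 samples and the Cycle 7 Day 1 preinfusion sample are already scheduled, and Section 7.8.1 requires exact dates and times to be recorded.

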APPENDIX D. EASTERN COOPERATIVE ONCOLOGY GROUP PERFORMANCE STATUS

Grade	Performance Status
0	Fully active, able to carry on all predisease performance without restriction
1	Restricted in physically strenuous activity but ambulatory and able to carry out work of a light or sedentary nature, eg, light house work, office work
2	Ambulatory and capable of all selfcare but unable to carry out any work activities. Up and about more than 50% of waking hours
3	Capable of only limited selfcare, confined to bed or chair more than 50% of waking hours
4	Completely disabled. Cannot carry on any selfcare. Totally confined to bed or chair
5	Dead

Source: [Oken et al 1982](#).

# LIST OF ABBREVIATIONS

| Abbreviation         | Term  |  |
|----------------------|---|--|
|                      |   |  |
| AE                   | adverse event   |  |
| AUC                  | area under the concentration-time curve   |  |
| AUC (0-t) | AUC from time zero (predose) to time of last observed quantifiable concentration within a subject across all treatments |  |
| CI                   | confidence interval   |  |
| $C_{max}$            | maximum observed concentration  |  |
| $C_{min}$            | minimum observed concentration  |  |
| CR                   | complete response   |  |
| CRF                  | case report form  |  |
| CSR                  | Clinical Study Report   |  |
| CTCAE                | Common Terminology Criteria for Adverse Events  |  |
| CTEP                 | Cancer Therapy Evaluation Program   |  |
| DLT                  | dose-limiting toxicity  |  |
| DOR                  | duration of response  |  |
| ECG                  | electrocardiogram   |  |
| ECOG                 | Eastern Cooperative Oncology Group  |  |
| EOS                  | end of study  |  |
| ЕОТ                  | end of treatment  |  |
| FAS                  | full analysis set   |  |
| FDA                  | Food and Drug Administration  |  |
|                      |   |  |
| irAE                 | immune-related adverse event  |  |
| JTc                  | corrected JT interval   |  |
| KM                   | Kaplan-Meier  |  |
| MedDRA               | Medical Dictionary for Regulatory Activities  |  |
| MNTD                 | maximum number of tolerated doses   |  |
| mRECIST              | modified Response Evaluation Criteria in Solid Tumors   |  |
| MSI                  | microsatellite instability  |  |
| MSKCC                | Memorial Sloan Kettering Cancer Center  |  |
| MTD                  | maximum tolerated dose  |  |
| NE                   | not evaluable   |  |
| NSCLC                | non-small cell lung cancer  |  |
| ORR                  | objective response rate   |  |

| Abbreviation     | Term   |  |
|------------------|--|--|
| PAD              | pharmacologically active dose  |  |
| PD               | progressive disease  |  |
| PD-1             | programmed death-1   |  |
| PD-L1            | programmed death ligand-1  |  |
| PFS              | progression-free survival  |  |
| PK               | pharmacokinetic  |  |
| PP               | per protocol   |  |
| PR               | partial response   |  |
| PT               | preferred term   |  |
| Q14D             | every 14 days  |  |
| Q21D             | every 21 days  |  |
| Q28D             | every 28 days  |  |
| QTcF             | QT interval corrected using the Fridericia formula   |  |
| QRS              | QRS is the combination of three of the graphical deflections on an ECG. It is usually the central and most visually obvious part of the tracing. It corresponds to the depolarization of the right and left ventricles of the human heart. |  |
| RCC              | renal cell carcinoma   |  |
| RECIST           | Response Evaluation Criteria in Solid Tumors   |  |
| RP2D             | recommended Part 2 dose  |  |
| RR               | RR is the interval from the beginning of a QRS complex to the beginning of the next QRS complex  |  |
| SAE              | serious adverse event  |  |
| SAP              | Statistical Analysis Plan  |  |
| SD               | stable disease   |  |
| SI               | International System of Units  |  |
| SOC              | system organ class   |  |
| t                | time of last observed quantifiable concentration   |  |
| TEAE             | treatment-emergent adverse event   |  |
| T max | time of occurrence of C max   |  |
| WHO              | World Health Organization  |  |

#### 1. INTRODUCTION

This is a Phase 1/2, open-label, nonrandomized, multicenter, dose-escalation study. This study will be conducted in 2 parts. Part 1 will utilize a 3 + 3 design to determine the MTD or PAD for INCAGN01876 in subjects with advanced or metastatic solid tumors. Part 2 of the study will further evaluate the safety, tolerability, preliminary efficacy, PK,

RP2D and schedule of INCAGN01876 in subjects with advanced or metastatic adenocarcinoma of the endometrium, melanoma, NSCLC (squamous and nonsquamous), and RCC. Section 1 of the Protocol provides a detailed description of the investigational product, target patient population, rationale for doses to be examined, and potential risks and benefits of treatment with INCAGN01876.

The purpose of this SAP is to provide details of the statistical analyses that have been outlined in the Study INCAGN 1876-101 Protocol. The scope of this plan includes the interim and final analyses that are planned and will be executed by the Department of Biostatistics or designee and the analyses of PK.

## 2. STUDY INFORMATION, OBJECTIVES, AND ENDPOINTS

## 2.1. Protocol and Case Report Form Version

This SAP is based on INCAGN 1876-101 Protocol Amendment 2 dated 24 OCT 2016 and CRFs approved 02 MAY 2016. Unless superseded by an amendment, this SAP will be effective for all subsequent Protocol amendments and CRF versions.

# 2.2. Study Objectives

## 2.2.1. Primary Objective

 To evaluate the safety, tolerability, and DLTs of INCAGN01876, and to define a MTD or PAD of INCAGN01876 in subjects with advanced or metastatic solid tumors.

### 2.2.2. Secondary Objectives

- To evaluate the PK of INCAGN01876 in subjects with advanced or metastatic solid tumors.
- To evaluate the preliminary efficacy of INCAGN01876 by assessing ORR, DOR, and rate of disease control per RECIST v1.1 and modified RECIST v1.1 (further referred to as mRECIST v1.1).
- To evaluate the preliminary efficacy of INCAGN01876 by assessing PFS per RECIST v1.1 and mRECIST v1.1.

## 2.2.3. Exploratory Objectives

## 2.3. Study Endpoints

## 2.3.1. Primary Endpoint

 Safety and tolerability will be assessed by monitoring frequency, duration, and severity of AEs.

## 2.3.2. Secondary Endpoints

- The PK of INCAGN01876 including Cmax, tmax, Cmin, and AUC0-t for subjects in Parts 1 and 2 will be summarized.
- ORR, defined as the percentage of subjects having CR or PR, will be determined by investigator assessment of radiographic disease assessments per RECIST v1.1 and mRECIST v1.1.
- DOR, defined as the time from earliest date of disease response (CR or PR) until
  earliest date of disease progression, will be determined by investigator assessment of
  radiographic disease assessments per RECIST v1.1 and mRECIST v1.1, or death due
  to any cause if occurring sooner than progression.
- Duration of disease control (CR, PR, and SD), as measured from first report of SD or better until disease progression, will be determined by investigator assessment of radiographic disease assessments per RECIST v1.1 and mRECIST v1.1, or death due to any cause if occurring sooner than progression.
- PFS, defined as the time from date of first dose of study drug until the earliest date of
  disease progression, will be determined by investigator assessment of objective
  radiographic disease assessments per RECIST v1.1 and mRECIST v1.1, or death due
  to any cause if occurring sooner than progression.

## 2.3.3. Exploratory Endpoints

[figure not shown]
## 3. STUDY DESIGN

This is an open-label, nonrandomized, Phase 1/2 study to determine the safety and tolerability, define the MTD or PAD, and assess the preliminary efficacy of INCAGN01876 in subjects with advanced or metastatic solid tumors. Subjects will receive escalating doses of INCAGN01876 on Day 1 of each cycle. Part 1 of the study will begin with 14-day cycles; however, alternate dose administration schedules may also be explored depending on PK, and safety results. The study will be conducted in 2 parts:

- Part 1 Dose Escalation and Safety Expansion will determine the PAD, defined as a dose that provides a maximal biochemical effect, or an analysis and/or the MTD of INCAGN01876, including defining the optimal dose administration schedule and the MNTD.
- Part 2 Dose Expansion will evaluate the RP2D and administration schedule determined in Part 1 in subjects with select tumor types including adenocarcinoma of endometrium, melanoma, NSCLC, and RCC.

See Figure 1 for overall study design.

Figure 1: Study Design

\*Part 1 will utilize a 3 + 3 design. For each dose cohort, there will be a safety observation period of 48 hours after the first subject is administered the first dose before enrollment of additional subjects is permitted.

†The Part 2 dose will be selected from 1 of the safety expansion doses and schedules explored.

# 3.1. Dose Escalation and Expansion

#### 3.1.1. Part 1 – Dose Escalation

in Table 3 of the Protocol.

The PAD is defined as a dose that provides a maximal biochemical effect, or

A DLT will be defined as the occurrence of a toxicity, with the exception of events clearly associated with the underlying disease, disease progression, a concomitant medication, or comorbidity; the list of toxicities that will be designated as dose limiting toxicities are provided

In Part 1 of the study, the MTD will be defined as 1 dose level below that at which  $\geq$  one-third of subjects in a particular cohort have DLTs.

In Part 1, subjects with advanced or metastatic solid tumors who progressed after treatment with available therapies that are known to confer clinical benefit, who are intolerant to treatment, or refuse standard treatment will be enrolled.

In the dose-escalation part of the study, a 3 + 3 design will be used to determine the MTD or PAD of INCAGN01876. A minimum of 3 evaluable subjects will be enrolled in each cohort

\*\*If Cohort 1 (0.03 mg/kg) exceeds the MTD, Cohort -1 (0.01 mg/kg) may be tested and/or Cohort 1 (0.03 mg/kg) will be tested at alternate dose schedules based on available safety, PK, data. If an alternate schedule is tested and determined to be safe, re-escalation of INCAGN01876 will proceed as outlined above.

†The safety expansion cohorts will confirm the preliminary safety of the highest dose levels determined to be safe or doses determined to be pharmacologically active. Alternate dose schedules may also be tested depending on PK,

beginning with Cohort 1 (0.03 mg/kg; starting dose). There will be a waiting period of 48 hours between dose administration of the first subject and second subject of each dose cohort. The first 3 subjects enrolled within a cohort will be observed for a DLT observation period of 28 days before the next cohort begins enrollment. The dose will be escalated if 0 of the first 3 evaluable subjects enrolled has a DLT. If 1 of the first 3 evaluable subjects enrolled has a DLT, then the cohort will be expanded to include 3 additional evaluable subjects, and if no DLT occurs in the additional 3 subjects, then the dose will be escalated. If a DLT occurs in one-third or more of the expanded cohort, then the MTD will be deemed to be exceeded, and the prior dose level will be considered the MTD. If only 3 subjects were treated at the MTD or PAD, then a minimum of 3 additional subjects will be enrolled before this dose is administered in Part 2 of the study.

If Cohort 1 (0.03 mg/kg; starting dose) exceeds the MTD, the sponsor and investigators will consider dosing INCAGN01876 at 0.01 mg/kg (Cohort -1), and/or investigate 0.03 mg/kg at alternate dose schedules, based on available safety, PK, data. If an alternate schedule is tested and determined to be safe, re-escalation of INCAGN01876 will proceed according to Table 1.

Throughout the treatment period, if > 33% of subjects (a minimum of 6 subjects) experience a  $\ge$  Grade 3 toxicity related to study drug after completing  $\ge$  4 cycles, then dose administration will be stopped, and the MNTD will be determined in conjunction with the investigators and sponsor based on all available safety data.

[figure not shown]
Additional subjects will be enrolled in a cohort to achieve the minimum of 3 evaluable subjects. Subjects who drop out for reasons other than a DLT (eg, events clearly associated with the underlying disease, disease progression, concomitant medication, or comorbidity) during the 28-day DLT observation period will be considered nonevaluable and will be replaced. Dose modifications should not be made during the DLT observation period without discussion with the medical monitor. Intrasubject dose escalation is not permitted; however, once the RP2D and schedule has been determined, ongoing subjects in Part 1 may be permitted to escalate to the RP2D with approval of the medical monitor. The cohorts and dose levels are shown in Table 1.

| Table 1. | INCAGN01876 Dose I    | l ovole and | Caharte |
|----------|-----------------------|-------------|---------|
| Table 1: | INCACTIONA / O DOSE I | Leveis and  | Comoris |

| Cohort            | Dose of INCAGN01876     |
|-------------------|-------------------------|
| -1                | 0.01 mg/kg a |
| 1 (starting dose) | 0.03 mg/kg              |
| 2                 | 0.1 mg/kg               |
| 3                 | 0.3 mg/kg               |
| 4                 | 1.0 mg/kg               |
| 5                 | 3.0 mg/kg               |
| 6                 | 5.0 mg/kg               |
| 7                 | 10.0 mg/kg              |

<sup>a Subjects who require a dose reduction below 0.01 mg/kg should be discontinued from study drug.

